Title: FitEx for Endometrial Cancer Survivors: Initial Efficacy

NCT trial number: NCT05737745

November 22, 2024

Study Protocol:

Overview:

This study targets 30 endometrial cancer survivors (ECS) and 2-5 support team members per ECS enrolled in intervention groups. We will use a 3-group design [FitEx (intervention 1) versus FitEx+yoga (intervention 2) versus standard-of-care (control)] with 3 assessments (pre, post [after 8-week program], and follow-up [6-month]). All participants will be given the option to receive a Fitbit Charge 5™ to objectively measure moderate-vigorous physical activity. ECS randomized to either intervention arm will participate in the 8-week FitEx program with their support team members which includes goal setting, self-monitoring, and weekly 30-minute synchronous sessions via Zoom. ECS in the control group will receive a one-time educational newsletter and will not recruit support team members. This protocol will be completed twice, once in 2023 and once in 2024.

OBJECTIVES:

- Aim 1: Among ECS, compare changes in objective MVPA between intervention groups and usual care (FitEx vs. control and FitEx+yoga vs. control) at 8 weeks.
- Aim 2: Among ECS, compare secondary efficacy outcomes and maintenance.
 - Aim 2a: Examine changes in secondary efficacy outcomes [e.g., quality of life (QOL), self-compassion, flourishing, self-efficacy, social support, habituation of exercise, and fruit/vegetable consumption] between intervention and usual care conditions (FitEx versus control and FitEx+yoga versus control) at 8 weeks.
 - Aim 2b: Explore maintenance of MPVA and secondary outcomes between intervention versus usual care (FitEx vs. control and FitEx+yoga vs. control) at 6 months.
- Aim 3: Among support team members, compare changes in MVPA and secondary outcomes (listed above) between intervention groups (FitEx vs. FitEx+yoga) at 8 weeks and 6 months.

RECRUITMENT:

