If an ECS is interested in participating, research study personnel will conduct a screening assessment and informed consent process either in-person or virtually. If conducted in-person, the informed consent process documents will be stored in the study coordinator’s office at Carilion Clinic. If conducted virtually, the informed consent process will be documented within REDCap. Participants may be consented on REDCap either over the phone or via teleconference depending on their preference. Consents conducted via teleconference will use secure, password protected Microsoft Teams or WebEx platforms. Zoom will not be used to consent participants. Support team members will undergo the same consent process as ECS after follow-up call and screening. All participants will be provided ample time to decide if they would like to join the study. There will be multiple opportunities for the participant to opt out before enrollment. Prior to consent, all potential participants will be sent a copy of the consent form for their review. A phone call or secure, web-based teleconference will be scheduled for interested participants to fill out the econsent via REDCap.

RANDOMIZATION & GROUPS

Each ECS who enrolls in the study will be randomized into one of three groups:

1. Standard-of-care (control)
2. FitEx intervention (FitEx-ECS)
3. FitEx intervention with integrated yoga principles (FitEx-ECS+yoga)

Overall, this study targets 10 ECS per group (30 total ECS) with 2-5 support team members per ECS in each intervention group (approximately 30 total support team members in each intervention group) yearly, for 2 years (90 participants per year, 180 participants total). All participants will be given the option to receive a Fitbit Charge 5™ to objectively measure moderate-vigorous physical activity.

Control Group:

ECS in the control group will be given the option to receive a Fitbit and will be sent a one-time educational newsletter about survivorship PA and nutrition recommendations. Control group participants will fill out all questionnaires at baseline, post, and 6-months follow up. Control

group participants will not recruit support team members, fill out FitEx-specific forms, nor participate in weekly Zoom sessions.

Intervention Groups:

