ECS randomized to either intervention arm will participate in the 8-week FitEx program adapted for ECS with their support team members. The FitEx-ECS intervention will entail group dynamics, goal setting, self-monitoring (tracking physical activity and fruit and vegetables intake via the FitEx-ECS portal within Fitabase or the FitEx Individual Log form), and feedback on goal attainment. The FitEx-ECS+yoga intervention will entail postures, breathwork, and mindfulness in addition to group dynamics, goal setting, self-monitoring (tracking physical activity and fruits and vegetables intake via the FitEx-ECS portal within Fitabase), and feedback on goal attainment. Each participant of either intervention group will have the option to receive Fitbit Charge 5TMs, fill out repeated program forms and questionnaires, and read weekly group-specific newsletters. Participants in either intervention will not have to pay any intervention program-related fees.

Additionally, all participants will be asked to report their weight during the baseline, post-program, and 6-month follow up questionnaires packet (see updated questionnaires document). Participants may also choose to report their weight using the FitEx-ECS portal within Fitabase.

Participants from both intervention groups will also be strongly encouraged to attend weekly group-specific 30-minute synchronous Zoom sessions consisting of virtual physical activity and social support with other teams. Topics for both intervention groups are similar, however the FitEx-ECS+yoga group's newsletter and virtual sessions are guided by yoga principles and mindfulness. Participants in the Zoom sessions will be verbally reminded of the audio recording at the beginning of each session. Participants may choose to turn on or off their cameras according to what is most comfortable.

SMS Reminders to Sync:

Participants in all groups with Fitbit devices who have not synced their Fitbit devices after 6 days will receive up to a maximum of two automated SMS-based reminders per week.

- Prompt: "Please open your Fitbit app and sync this past week's activity."

Automated SMS-based prompts will be set up using the FitEx-ECS portal within Fitabase. Fitabase uses Azure Always Encrypted to encrypt phone numbers at rest and in transit to protect participant personal information.

COMPENSATION

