Due to the small sample size and exploratory nature of this pilot study, statistical analyses will be descriptive rather than inferential. However, we will determine if a signal exists between intervention and control groups regarding participants' physical activity using MET (metabolic equivalents) data from Fitbits. Weekly data will be compared at week-8 (intervention conclusion) to baseline. Data is considered appropriate if it was collected from at least 4 days per week. Data from missing days was input at "0". Students T-tests were used to compare means from each intervention group to the control condition for the primary outcome.

Attendance/Retention Measures

Participants who enroll in the study will be asked to attend weekly meetings. The attendance at the meetings will be recorded to assess the percentage of participants who are interested in weekly meetings. The acceptability of FitEx will be assessed in part using meeting attendance. Attendance and retention will be used as measures of intervention acceptability.

The number of support group members who attend each session will also be noted. The ratio of support group members to endometrial cancer survivor participants will also be noted.

We will examine our attrition rate and attendance as noted above. We will also reach out to participants who do not complete our study to determine the reasons for their decisions. Our study will be feasible in its current state if our attrition rate is between 10-27%.

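### The primary t-tests treat intervention survivors as independent although they share live arm-specific sessions; if activity correlates within session groups, a signal against control may be over-read

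*Combined protocol and SAP*

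**What the plan says.** - **Randomisation** (RANDOMIZATION & GROUPS): individual. "Each ECS who enrolls in the study will be randomized into one of three groups".
- **Primary contrast** (OBJECTIVES, Aim 1): "Among ECS, compare changes in objective MVPA between intervention groups and usual care", at 8 weeks, for each intervention arm separately.
- **Delivery in the intervention arms** (Intervention Groups): participants are "strongly encouraged to attend weekly group-specific 30-minute synchronous Zoom sessions consisting of virtual physical activity and social support with other teams". Group dynamics is also listed as a component.
- **Delivery in the control arm** (Control Group): "group participants will not recruit support team members, fill out FitEx-specific forms, nor participate in weekly Zoom sessions".
- **Size** (RANDOMIZATION & GROUPS): "Overall, this study targets 10 ECS per group (30 total ECS"), with the headcount stated yearly for two years. The Overview gives 30 survivors as the study target and says the protocol is carried out once in 2023 and once in 2024.
- **Analysis** (STATISTICAL ASSESSMENT: Measures): "statistical analyses will be descriptive rather than inferential". The next sentence nevertheless says the team will determine whether a signal exists, and the paragraph ends "Students T-tests were used to compare means from each intervention group to the control condition for the primary outcome".

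The plan mentions no ICC, session-group term or term for run.

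**The concern.** This is a partially nested design. Survivors in an intervention arm exercise and support one another in a shared live session, and controls have no such contact. A Student t-test assumes that observations are independent in both samples. If a session group goes especially well or badly, its members move together. The t-test counts that shared movement as several independent pieces of evidence.

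What is at stake is how the pilot's main result is read. This is the primary outcome, and no other analysis in the plan has a named test. A term for run common to all arms would not absorb the shared effect, because that effect exists only in the intervention arms.

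**Working it through.** **Reproducing the stated figure.** The only sample-size figure is the headcount: 10 x 3 survivors + 30 x 2 support members = 90 per year, and 90 x 2 = 180. This matches. No alpha, power, standard deviation or ICC is given, so no error rate can be reproduced from the plan.

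**Inputs from the documents**
- Survivors per arm and run, m: 10 if 30 survivors enter each year (the reading that fits 90 and 180). If 30 is the total over both runs, as the Overview can be read, m = 30 / 3 / 2 = 5.
- Session groups per arm: at least one per run, so at least two over the study.
- Attrition: 10-27% (feasibility criterion). At the upper end 10 x 0.73 = 7.3, so about 7 remain per group.

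**Assumptions**
- One session group per arm and run. The number of weekly session slots is not stated; more slots would make m smaller.
- Independent controls and equal total variance in both arms.
- A two-sided 5% level.
- ICC of 0, 0.02, 0.05 or 0.10.

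**Formulae.** The design effect applies in the intervention arm only: DE = 1 + (m - 1) x ICC. The true variance of the difference is SD² x (DE/n_int + 1/n_ctrl). With equal arms, the interval must widen by the factor √((DE + 1)/2).

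| m | ICC | DE | √((DE+1)/2) | True error at nominal 5% |
|---|---|---|---|---|
| 10 | 0 | 1.00 | 1.000 | 5% |
| 10 | 0.02 | 1.18 | 1.044 | about 6% |
| 10 | 0.05 | 1.45 | 1.107 | about 7.7% |
| 10 | 0.10 | 1.90 | 1.204 | about 10.5% |
| 5 | 0.02 | 1.08 | 1.020 | about 5.5% |
| 5 | 0.05 | 1.20 | 1.049 | about 6.2% |
| 5 | 0.10 | 1.40 | 1.095 | about 7.4% |

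The error rates come from simulated pooled t-tests (at least 100,000 replicates per row) with zero mean effect and a random session-group effect in the intervention arm. With about 7 left per group they are about 6.8% at ICC 0.05 and 8.7% at 0.10. For a single run of 10 v 10 they are about 7.7% and 10.7%, so pooling the two runs hardly changes them.

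**A second, smaller effect.** Correlation also shrinks the sample variance within the intervention arm, whose expectation is SD² x (n - DE)/(n - 1). For two groups of 10 at ICC 0.05, in SD units:
- True SE: √(1.45/20 + 1/20) = 0.350.
- Expected intervention-arm variance: (20 - 1.45)/19 = 0.976. Pooled with the control variance of 1, this is 0.988.
- t-test SE: √(0.988 x 2/20) = 0.314.
- Ratio: 0.350/0.314 = 1.11.

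At ICC 0.10 the same calculation gives 1.22.

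**Check of the fix.** Multiplying the intervention-arm variance by DE, with the ICC correctly assumed and 10 per group, brings the error back to about 5.2-5.8% at ICC 0.05 and 0.10.

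**The case against.** **The analyses are declared descriptive.** The plan states no alpha, interval or power, so there is no promised error rate to breach. That stands, and the 5% level above is only a yardstick. It does not remove the point, because the same paragraph sets out to find a signal and names a test for doing so.

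**The result depends on which null is meant.** Randomisation is individual. If the programme and its sessions changed nobody's activity, there would be no session effect and the t-test would keep about its nominal size. The inflated rates refer to a zero average effect over session groups, when particular groups may still move. Treating the session groups as fixed is defensible for describing the programme as delivered. It does not answer whether another session group would respond alike. That question matters here, since the plan runs the programme twice and invites controls to future iterations.

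**Shared exposure is limited.** Contact is 30 minutes a week, attendance is not compulsory, and absentees are offered an instructor-only video. Group dynamics may refer to each survivor's own support team, which would not link survivors. Fitbits are optional and a week needs at least 4 days of data, so the analysed m may be well under 10. All this lowers the effect without removing it.

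**Stronger readings.** A reader might infer that the standard errors are definitely too small, or that each arm is one group throughout the study. The documents give no ICC, and with two runs there are at least two groups per arm. A reader might also infer that clustering of support members invalidates Aim 1; it does not, because Aim 1 covers survivors only and each brings a separate team.

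**Conclusion.** The point holds conditionally. The plan makes no allowance for shared sessions in the intervention arms, and any positive correlation within session groups makes the standard error of each arm-v-control contrast too small. The size cannot be determined from the documents: the effect is absent at ICC 0, slight at 0.02 and noticeable from about 0.05. The figures for 10 per group are near the upper end of what the design allows, provided there is one session group per arm and run. The lower figures apply if 30 survivors is the total over both runs. The consequence is an over-read signal in a pilot, not a failed confirmatory test.

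**What to change.** In STATISTICAL ASSESSMENT: Measures:

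1. Report each arm-v-control difference with a 95% confidence interval.
2. As a sensitivity range, repeat the interval with the intervention-arm variance multiplied by 1 + (m - 1) x ICC at ICC 0, 0.05 and 0.10. Here m is the number of survivors analysed per session group, and the control variance is not inflated.
3. Show the 2023 and 2024 differences side by side.
4. State that the ICC is assumed, because one or two session groups per arm cannot estimate it, and that any signal is read in the light of this range. A mixed model would not get round this, for the same reason.
5. State the number of session groups per arm and run, and reconcile the Overview's 30 survivors with the yearly headcount, since m depends on both.

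Add no pass/fail rule at a particular ICC; nothing in the documents supports one value over another.

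The cost is a few lines of text and simple arithmetic. For m of 5 to 10, intervals widen by about 5-10% at ICC 0.05 and 10-20% at ICC 0.10.
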